# 17. Immune Monitoring for Phase I/IIa anakinra study

PBMC will be separated by Ficoll Hypaque from KD subjects at three time points (pre-treatment, 2 weeks, and 6 weeks post-treatment) for staining with specific monoclonal antibodies (MoAbs) to characterize DC lineages, macrophages and their activation/maturation stage. Anti-DR (MHC class II molecules) and anti-CD86 define maturity and activation. CD11c defines the DC lineage, and is not expressed on macrophages. Antibodies anti-CD11c will be used in combination with anti-DR and anti-CD86 and other markers, well described in the literature. Briefly: to define myeloid DC: anti-CD11b, (also expressed on macrophages but negative in plasmacytoid DC and thymic DC) and anti-BDCA-1. To define immature tolerogenic myeloid DC very relevant in the immune-regulation in KD, we will look at CD14, co-expressed on macrophages but not on plasmacytoid DC, in CD11c + CD11b + myeloid DC. Macrophages will be identified by the expression of CD11b and CD14 in CD11c negative cells. To enumerate activated CD4+ and CD8+ T cells and regulatory T cells (Treg) we will use anti-

CD4, anti-CD8, anti-DR, anti-CD25 (Treg are CD25high) and anti-IL-7 receptor, expressed on proinflammatory cells and peripherally-induced Treg but not in natural Treg.

# 18. Measures of Activity

#### 18A. Measures of inflammation for Phase I/IIa anakinra study

Transcript abundance will be measured in whole blood by microarray. Levels of hsCRP,  $\alpha$ -1antitrypsin and fibrinogen, and the WBC and ESR will be measured in the hospital clinical laboratory. Levels of TNFaR1 and R2, IFNg, IL-1 RAP, IL-1R1 and R2, MMP9, caspase-1, IL-6R, IL-18RAP, IL-12, sIL-2R, TGFb and IL-10 will be measured by ELISA. Results of transcript abundance and measures of inflammation will be compared to database controls from the KD Research Center (>600 KD patients with available RNA and plasma samples in our biorepository) matched (1 case: 2 controls) by age (± 2 yrs. with lower limit of 2 yrs.), sex, and coronary artery Z-score.

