# Specific Aim 2 will describe the pharmacokinetics of anakinra and test the hypothesis that anakinra will decrease systemic and coronary artery inflammation associated with acute KD.

Blood will be tested pre-drug administration, 48 hours after initiation of therapy and at 2 weeks and 6 weeks for markers of inflammation and enumeration of dendritic cells and T cells. Echocardiographic assessment of CAA at these time points will be compared to historical controls matched for age, sex, illness day at diagnosis, and coronary artery status on initial echo.

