### 11B. Inclusion

#### 11B1. Inclusion for Phase I/IIa anakinra study

- Meets clinical criteria for KD according to American Heart Association guidelines (Table 4): Fever (T≥38°C or 100.4°C) ≥ 3 days and ≥ 2 clinical criteria with LAD or RCA z-score ≥ 2.5
- 2. Patient is at least 28 days old
- 3. Patient presents within the first 20 days after fever onset
- 4. Parent or legal guardian able and willing to provide informed consent
- 5. Able to be dosed between 20 mg (min amount on syringe) and 200 mg at 8 mg/kg/day

Dose escalation level*	Minimum subject weight to administer 20 mg	Maximum subject weight to administer 200 mg
8 mg/kg	2.5 kg	25 kg

\*This table includes only the 8 mg/kg dose level as enrollment in the 4 and 6 mg/kg cohorts has been completed as of the Nov 2016 revision.

\*As of the August 2017 revision, we have enrolled 2 subjects at 8mg/kg/day without any dose limiting toxicities.

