#### 11B2. Inclusion for Combination therapy pilot study

- 1. Meets clinical criteria for KD according to American Heart Association guidelines (**Table 4**): Fever (T≥38°C or 100.4°C) ≥ 3 days and ≥ 2 clinical criteria with LAD or RCA z-score ≥ 2.5
- Patient at least 2yo and weighs ≤ 25 kg (weight limit based on anakinra max dose of 200 mg/day at a calculated dose of 8 mg/kg/day)
- 3. Patient presents within the first 20 days after fever onset
- 4. Parent or legal guardian able and willing to provide informed consent

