#### 11C. Exclusion

#### 11C1. Exclusion for Phase I/IIa anakinra study

- 1. Use of an IL-1beta antagonist within the 3 months prior to enrollment
- 2. Have any chronic disease, except asthma, atopic dermatitis, autism or controlled seizure disorder
- 3. Patient has a history of hypersensitivity to anakinra
- 4. Personal or immediate family history of tuberculosis (TB) or TB exposure
- 5. Active, culture-positive bacterial infection
- Baseline Scr ≥ 0.50 mg/dL (28 days old to 1 year old) or an eGFR lower than 45 mL/min/1.73m^2 (≥ 1 year old)

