#### 19B. Statistical analysis of inflammatory studies

**19B1. Statistical analysis of inflammation studies for Phase I/IIa anakinra study** The objective of this matched case-control study is to determine the activity profile of anakinra in the treatment of KD subjects with CAA. Measures of inflammation will be compared to that of matched controls via paired statistical tests (e.g. McNemar's test for categorical outcomes or the paired t-test for continuous outcomes). Non-parametric alternatives will be considered only if distributional assumptions are violated.

**Control Group:** Controls will be chosen from the >600 subjects with data in our web-based data repository in REDCap. Controls will be matched to study patients based on age, sex, Illness Day at diagnosis, and baseline Z score.

**Analysis:** Each marker will be initially summarized descriptively and analyzed individually. Separate multivariable mixed effects regression modeling for clustered data (to account for the case-control paired nature of samples) will be used to characterize the markers of anakinra-treated subjects versus matched controls to adjust for any known confounders and additional time points (baseline, 48 hours, 2 weeks, and 6 weeks). In addition, any covariate at the individual level that is simultaneously unbalanced and associated with the outcome will be included in the model. Covariates of interest include demographic variables (e.g., ethnicity, Illness Day at diagnosis, response to IVIG therapy). Permutation tests may be implemented to verify that valid p-values will be obtained even if model assumptions are not correct. Note that the mixed model seamlessly accommodates different times of measurement (e.g. 2-week and 6-week time points) as well as missed measurements and data from subjects who are lost to follow-up. A corresponding Generalized Estimating Equations (GEE) model will be used as the sensitivity analysis method. An analogous secondary model including all subjects in this study will also be considered to examine the dose versus activity relationship. In this model, dosage will be included as a covariate to examine any dosage trend in activity.

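### The control-matching rule in Section 18A sets a 2-year minimum age, but the anakinra study enrols from 28 days, so no case under 2 can have a same-age control

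*Combined protocol and SAP*

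**What the plan says.** Section 18A compares transcript abundance and inflammation markers in anakinra-treated subjects with controls from the research centre's repository, "matched (1 case: 2 controls) by age (± 2 yrs. with lower limit of 2 yrs.), sex, and coronary artery Z-score".

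The Phase I/IIa anakinra study plans for infants. An inclusion criterion in 11B1 reads "Patient is at least 28 days old", and 11C1 sets a separate creatinine limit for the band "28 days old to 1 year old". Only the combination pilot starts at 2 years; the criterion in 11B2 begins "Patient at least 2yo and weighs".

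Two other places describe matching for the anakinra study, and neither states an age band or a floor:

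- Aim 2 in Section 9A, for the echocardiographic comparison: "historical controls matched for age, sex, illness day at diagnosis, and coronary artery status on initial echo".
- The Control Group paragraph of 19B1, for the marker analysis: "Controls will be matched to study patients based on age, sex, Illness Day at diagnosis, and baseline Z score".

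On adjustment, 19B1 says that "any covariate at the individual level that is simultaneously unbalanced and associated with the outcome will be included in the model", and then: "Covariates of interest include demographic variables (e.g., ethnicity, Illness Day at diagnosis, response to IVIG therapy".

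**The concern.** A floor of 2 years on control age cannot give a close age match to a case younger than 2. Every such case is paired with older children, so the mismatch runs in one direction and does not average out over pairs. Section 18A also omits illness day, which 19B1 requires, so a reader cannot tell which rule governs.

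The comparison at stake is the only one that sets anakinra-treated marker results against patients not given anakinra, and 15A sizes the study on it. Safety, dose escalation, pre/post analyses, the dose-activity model and the echo comparison described in Aim 2 do not depend on the floor.

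Section 15A compares change scores, so a constant age difference in marker level cancels. Bias arises if age affects how a marker changes over the illness, or where post-baseline levels are compared directly.

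**Working it through.** **The plan's own figure.** Section 15A states 80% power with 18 cases and 18 matched controls, using a two-sided paired t-test at alpha 0.05. I took the stated SD as the SD of the paired difference and computed exact power from the noncentral t, with 17 degrees of freedom and noncentrality d × √18.

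- IL-1RAP: d = 2.2/3.2 = 0.6875, noncentrality 2.92, power 78.5%.
- IL-1R1: d = 5.6/8 = 0.70, noncentrality 2.97, power 79.9%.

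Both are close to the stated 80%; reaching it in full takes 19 pairs. The floor does not alter this calculation. It alters who the controls are.

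**Age windows.** Inputs are the ±2-year band and 2-year floor (18A) and the minimum case age of 28 days, or 0.077 years (11B1). For a case aged *a* years:

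- Window under 18A: max(2, *a* − 2) to *a* + 2.
- Smallest case-control gap: max(0, 2 − *a*). For cases under 2 the largest gap is 2 years.
- Window midpoint minus case age, for *a* < 4: (2 + *a* + 2)/2 − *a* = 2 − *a*/2.
- Comparison window without the floor: max(0.077, *a* − 2) to *a* + 2.
- Share of the age window removed: 1 − (width with floor)/(width without).

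| Case age | Controls under 18A (years) | Smallest gap | Midpoint excess with floor | Share of window removed |
|---|---|---|---|---|
| 28 days | 2.00–2.08 | 23 months | 1.96 y | 1 − 0.077/2.000 = 96% |
| 6 months | 2.0–2.5 | 18 months | 1.75 y | 1 − 0.500/2.423 = 79% |
| 1 year | 2–3 | 12 months | 1.5 y | 1 − 1.000/2.923 = 66% |
| 23 months | 2.00–3.92 | 1 month | 1.04 y | 1 − 1.917/3.840 = 50% |
| 3 years | 2–5 | 0 | 0.5 y | 1 − 3/4 = 25% |

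Cases aged 2 to under 4 can have same-age controls, but their window still leans older.

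**How much is due to the floor.** A ±2-year band cut at 28 days also leans older for infants. Its midpoint excess is 1.00 y at 28 days, 0.79 y at 6 months and 0.54 y at 1 year. The floor therefore adds 1.96 − 1.00 = 0.96 y, 1.75 − 0.79 = 0.96 y and 1.5 − 0.54 = 0.96 y.

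**Other readings.** If the 2-year figure were a limit on the tolerance, it would only repeat the ±2 years. If the floor were meant only to trim the band for older cases, 18A would give no usable rule below age 2. If cases under 2 were left out of the comparison, pairs would be lost. The documents do not give the share under 2; assuming 10% to 50% of 18, 16 down to 9 pairs remain and IL-1RAP power falls to between 73% and 44%.

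**The case against.** The strongest reply is that 19B1 already provides for age. It allows adjustment for known confounders, its covariates of interest include demographic variables, and 11D1 lists age at onset first under demographic data. It stands that age adjustment is foreseen, even though the examples in 19B1 do not name it. It does not repair the design: under the floor every observation below age 2 is a treated case, so adjustment there extrapolates from controls aged 2 or more.

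Second, Aim 2 and 19B1 say only that age is matched, so 18A could be read as the more detailed statement of the same rule. That is fair as far as the wording goes, but it leaves the floor in force for infants.

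Third, the shares removed are lengths on an age axis, not shares of available controls, and about half of the midpoint skew at 28 days remains without the floor. Both points are correct, and the figures should be read that way.

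Fourth, the markers are secondary outcomes, and no age effect on marker change is documented. This limits the severity and means that bias is possible rather than shown. It does not give a reason for the floor, and the documents offer none. A 2-year minimum would be consistent with entry to the combination pilot, but the pilot's own matching text in 18B and 19B2 contains no such floor.

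**Conclusion.** The concern holds. As written, 18A gives every anakinra case under 2 only older controls, with a smallest gap running from 23 months at the youngest enrolment age to 1 month at 23 months of age. These cases do have eligible controls, but never same-age ones. The conclusion rests on reading the 2-year figure as a minimum control age, which is the natural reading; the alternatives either repeat the tolerance or leave infants without a rule.

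The resulting bias in the marker comparison cannot be computed from the documents. It depends on how many cases are under 2 and on whether age modifies marker change, and neither is given. The point should be fixed because it affects the controlled marker comparison on which 15A is based. It does not affect the primary safety outcome.

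A separate discrepancy sits in the same sentence of 18A. Two controls per case means 36 controls for 18 cases, whereas 15A counts 18 and sizes a paired test. The conclusion above does not depend on it.

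**What to change.** - In 18A, for the anakinra study, delete the 2-year floor or set it at the 28-day enrolment minimum. Add illness day so that 18A, 19B1 and Aim 2 list the same matching variables.
- State that the nearest-age eligible control is taken, because ±2 years alone still leans older for infants. A tighter infant band is optional and depends on how many Z-score-matched infants the repository holds.
- Name age as a covariate in the 19B1 models.
- In the same edit, state one matching ratio in 15A and 18A. If 1:2 is kept, analyse by matched set, using the mean of the two controls or the planned mixed model with a matched-set effect, rather than a 1:1 paired t-test or McNemar's test.

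The cost is protocol and SAP wording only. Removing the floor widens the age window (from 0.08 to 2.00 years at 28 days, and from 0.50 to 2.42 years at 6 months), so it cannot make age matching harder. Matching on illness day does narrow the pool, but 19B1 already requires it. Because controls must also match on Z-score, the usable pool is well below the stated figure of more than 600, and some infants may have only one suitable control.

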# 18B. Measures of inflammation and endothelial cell function for Combination therapy pilot study

We will measure plasma levels of IL-1R accessory protein and soluble IL-1R1 from the study subjects and controls as surrogates for IL-1 $\alpha$  and IL-1 $\beta$ , which are not stable in patient plasma. To further assess inflammation, we will also measure the following pro-inflammatory cytokines in plasma: IL-17, IL-6, sIL-6R, TNF $\alpha$ R1, IFN $\gamma$ , as well as the anti-inflammatory cytokine IL-10. To assess the change in MMP9 activity that could be a direct effect of atorvastatin treatment, (Koh 2002, Massaro 2010) we will measure plasma MMP9 levels. Transcript levels in whole blood RNA (PAXgene® tubes) of all of the above analytes will be measured using a combination of TaqMan 5'nuclease Gene Expression Assays (Applied Biosystems) and the Inflammatory cytokine array (Qiagen). Relative abundance of the target transcripts will be normalized to the expression level of TAF1B, which has been validated as a housekeeping gene that is not upregulated in acute KD.(Popper 2007) Time points for all of the above studies will be baseline, 48 hr, and 2 wk posttreatment. Three different control groups with samples collected at similar time points will be matched from our KD biorepository at UCSD (>600 subjects); standard treatment alone (n=20), standard treatment+atorvastatin (n=10), and standard treatment+anakinra (n=10). Banked samples, including those from Phase I trials of both anakinra and atorvastatin, will allow us to match study patients on potentially important variables including age, sex, illness day at diagnosis, and baseline coronary artery damage as measured by echocardiogram.

Subject and control sera will be compared for suppression of the innate immune response by anakinra and restoration of EC function by atorvastatin. IL-1-TIFA-NLRP3 activation as well as levels of KLF4, miR-483, and EndoMT marker genes including CTGF in cultured human aortic ECs and mouse lung ECs with subject and control sera from baseline, 48 hr, and 2 wk post-treatment will be measured. Functional assays will also be performed including NO bioavailability and EC permeability. Induction of EndoMT will be compared using paired sera from pre-treatment and 2 wk time points while induction of an EC inflammatory response will be compared using pre-treatment and 48 hr post-treatment paired sera. These readouts of innate immune activation and EC function will be correlated with clinical data.

# **19. Statistical Analyses**

# 19A. Statistical analysis of safety for Phase I/IIa anakinra study and Combination therapy pilot study

Descriptive statistics will be calculated for demographic and baseline characteristics, variables related to biologic activity, immunologic variables, PK variables, and safety data. The study population will be described using summary descriptive statistics such as mean, median, standard deviation, and range for continuous variables and frequencies for categorical variables. All events (AEs, SAEs, and UPRs) will be recorded, documenting the course, outcome, severity, and

relationship to the study treatment. Incidence rates of events and the proportion of subjects prematurely withdrawn from the study due to events will be compiled. Analyses will be performed for all patients who have received at least one dose of study treatment. Deviation from the treatment plan will be recorded in the case report forms. The percentage of subjects failing to complete the study or discontinuing prematurely (as well as the times and reasons for discontinuation) will be reported. Refer to Section 12E for the operating characteristics of the Phase I dose escalation for the Phase I/IIa anakinra study.

#### 19B. Statistical analysis of inflammatory studies

**19B1. Statistical analysis of inflammation studies for Phase I/IIa anakinra study** The objective of this matched case-control study is to determine the activity profile of anakinra in the treatment of KD subjects with CAA. Measures of inflammation will be compared to that of matched controls via paired statistical tests (e.g. McNemar's test for categorical outcomes or the paired t-test for continuous outcomes). Non-parametric alternatives will be considered only if distributional assumptions are violated.

**Control Group:** Controls will be chosen from the >600 subjects with data in our web-based data repository in REDCap. Controls will be matched to study patients based on age, sex, Illness Day at diagnosis, and baseline Z score.

**Analysis:** Each marker will be initially summarized descriptively and analyzed individually. Separate multivariable mixed effects regression modeling for clustered data (to account for the case-control paired nature of samples) will be used to characterize the markers of anakinra-treated subjects versus matched controls to adjust for any known confounders and additional time points (baseline, 48 hours, 2 weeks, and 6 weeks). In addition, any covariate at the individual level that is simultaneously unbalanced and associated with the outcome will be included in the model. Covariates of interest include demographic variables (e.g., ethnicity, Illness Day at diagnosis, response to IVIG therapy). Permutation tests may be implemented to verify that valid p-values will be obtained even if model assumptions are not correct. Note that the mixed model seamlessly accommodates different times of measurement (e.g. 2-week and 6-week time points) as well as missed measurements and data from subjects who are lost to follow-up. A corresponding Generalized Estimating Equations (GEE) model will be used as the sensitivity analysis method. An analogous secondary model including all subjects in this study will also be considered to examine the dose versus activity relationship. In this model, dosage will be included as a covariate to examine any dosage trend in activity.

The above approach will be repeated for the other markers. That is, multi-level mixed effects regression models analogous to the above methodology will be applied for other markers: Levels of high sensitivity (hs) CRP, alpha-1 antitrypsin, TNFaR1 and R2, IFNg, IL-1 RAP, IL-1R1 and R2, MMP9, caspase-1, IL-6R, IL-18RAP, IL-12, IL-2, TGFb and IL-10.

Measures of transcript abundance will also be analyzed via microarray analysis. Data will be preprocessed first and then microarray analysis procedures will be used to measure abundance. The R software (version 3.0.2) and Bioconductor package in R will be used for the analysis. For coronary outcomes as assessed by echocardiography, we will compare the delta Z scores (baseline minus 2weeks and 6-weeks) between anakinra subjects and matched controls. A GEE model will be used as the sensitivity analysis method. Since this is a safety and early efficacy study, no adjustments for multiple comparisons will be made for biomarker analyses. P-values less than 0.05 will be considered statistically significant. All statistical analyses will be performed in R version 3.2.0 (www.rproject.org/). Similarly, analyses will be repeated on all subjects to characterize any dose-activity relationship, adjusting for dosage as a covariate in the model.

To determine the "best" or "set of best" markers that have the greatest improvement from baseline in anakinra-treated patients, ROC and AUROC analysis will be considered. In the event that there is

high multi-collinearity amongst the markers, we will adopt the "glmpath" approach, which is based on Least Angle Regression (LARS) methods to select the best biomarkers (Park 2007).

Missing data assumptions: The proposed mixed-effects regression model is consistent under the assumption that the outcome data are "missing at random" (MAR), that is, mixed models with a random effect assume only that the probability that an outcome is missing depends on observed outcomes. GEE models, which are proposed as a sensitivity analysis, assume that the outcome data are "missing completely at random", that is, that the probability that an outcome is missing does not depend on any previous, present or succeeding value of the outcome. This will enable us to assess the impact of the missing data mechanism on statistical inferences drawn from these models.

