## 11D. Data Collection

#### 11D1. Data collection for Phase I/lla anakinra study

#### 1. Demographic data:

- a. Patient's age at KD onset, sex, self-reported ethnicity of each biologic parent
- 2. Clinical data:
  - a. Physical findings confirming the KD case definition(Newburger 2004)
  - b. Illness day at study entry
  - c. Response to IVIG (IVIG-resistance will be defined as persistent or recrudescent fever (T≥38.0°C rectally) ≥36 h and < 7d following the end of the IVIG infusion (2g/kg) ([name] 2008).
  - d. Name, dose and indication of concomitant medications taken while on study
  - e. Complete white blood count (WBC), hsCRP, erythrocyte sedimentation (ESR), fibrinogen, and alpha-1-antitrypsin levels at baseline, 48 hours (not ESR as IVIG recently administered), 2 weeks and 6 weeks (if still on study drug) after drug administration
  - f. Serum creatinine at baseline prior to receiving study drug
  - g. Severity and duration of infections (with any associated cultures or diagnostic testing) during study
  - h. Echocardiographic data at baseline, 48 hours, and 2 and 6 weeks (standard of care for patients with CAA)

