#### 11G. Echocardiography Core Lab for Phase I/IIa anakinra study and Combination therapy pilot study

An echocardiogram will be performed at the following time points:

- During initial hospitalization (as soon after admission as possible)
- 48 hours after enrollment in this study
- Study week 2 (Study day 14 ± 7 days)
- Study week 6 (Study day 42 ± 7 days)

2-D transthoracic echocardiograms (2-D Echo) will be performed on all KD subjects according to a strict pre-determined protocol at standard of care time points. All echocardiographic images will be analyzed by [name], Director of Non-Invasive Cardiovascular Imaging at Rady Children's Hospital San Diego. She will be blinded to patient data and clinical status. [name] will also assure adherence to the echo protocols across all echocardiogram technicians. 2-D Echo will be performed at KD diagnosis (within 24h of IVIG infusion) and again at two and six weeks following enrollment with sedation when clinically indicated. The internal lumen diameters of the left main (LMCA), proximal and distal LAD, circumflex, posterior descending, and proximal and distal RCA will each be measured. Dimensions of the LMCA, proximal LAD, and proximal RCA will be adjusted for body surface area and expressed in standard deviation units (Z-scores) (Manlhiot 2009). A variable "Z worst any vessel" will be created to capture the maximal Z score of the RCA or LAD at any time point, as well as the Z-score of the LMCA if an aneurysm is present there with a Z-score larger than that of the RCA or LAD. Coronary artery aneurysm will be defined as a Z-score of 2.5 or larger of the RCA or LAD(Nishiike 2006).

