# 14. Additional Therapy for Phase I/IIa anakinra study and Combination therapy pilot study

#### 14a. Management of Treatment-resistant Subjects

Treatment-resistance will be defined as persistent or recrudescent fever ( $T \ge 38.0^{\circ}C$  rectally)  $\ge 36$  hours and <7 days following end of IVIG infusion. Subjects who meet criteria for treatment-resistance will be treated at the Center PI's discretion.

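### 19B1 and 19B2 let response to IVIG into the marker models with no pre-dose limit, although it can be settled after study drug starts

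*Combined protocol and SAP*

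**What the plan says.** The analysis paragraphs of 19B1 (Phase I/IIa anakinra study) and 19B2 (Combination therapy pilot study) compare treated subjects with matched historical controls in mixed models. The models are meant "to adjust for any known confounders and additional time points" (baseline, 48 hours, 2 weeks, 6 weeks), with a GEE model as sensitivity analysis. The entry rule is that "any covariate at the individual level that is simultaneously unbalanced and associated with the outcome will be included in the model". The candidates follow: "Covariates of interest include demographic variables (e.g., ethnicity, Illness Day at diagnosis, response to IVIG therapy".

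The data lists in 11D1 and 11D2 classify response to IVIG differently. Demographic data there are age, sex and parental ethnicity; response to IVIG is a clinical item: "IVIG-resistance will be defined as persistent or recrudescent fever", counted from 36 hours to under 7 days after the infusion ends. Section 14a uses the same window and expects such cases among enrolled subjects: "Subjects who meet criteria for treatment-resistance will be treated at the Center" PI's discretion.

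Controls are matched on age, sex, illness day at diagnosis and baseline Z score, but not on response to IVIG.

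**The concern.** Adjusting for a characteristic fixed before treatment can remove confounding. Adjusting for something that treatment may have changed can remove part of the treatment effect. The covariate sentence treats response to IVIG as the first kind; its definition allows it to be the second.

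Specific Aim 2 of the Phase I/IIa study is that "anakinra will decrease systemic and coronary artery inflammation associated with acute KD". If lower inflammation also means less fever, fewer treated subjects will be classed as resistant. The drug then helps to create the imbalance that the entry rule looks for, and inflammatory markers are likely to supply the association. A reader who sees the adjusted effect shrink could not tell whether confounding or drug effect had been removed. These models are the plan's adjusted estimates of marker activity.

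**Working it through.** **1. The plan's powered comparison.** Section 15A gives differences of 2.2 and 5.6 with pooled SDs of 3.2 and 8, so d = 2.2/3.2 = 0.6875 and 5.6/8 = 0.70. For a two-sided paired t-test at 0.05 with 18 pairs (17 df), taking the pooled SD as the SD of the paired difference, the noncentrality is d√18 = 2.917 and 2.970. Power is 78.5% and 79.9%, which agrees with the stated 80%. This test, like the paired t-test in 15B, carries no covariate, so response to IVIG cannot alter it.

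**2. Timing.** Let h be the hours from the end of IVIG to the first dose. The resistance window runs from 36 to 7 × 24 = 168 hours.

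- h below 36: nobody's status is known at the first dose.
- h from 36 to 168: subjects already febrile in the window are resistant; the others are undecided.
- h of 168 or more: every status is settled before dosing.

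The 48-hour marker sample falls at h + 48, so the window is still open then if h is below 168 − 48 = 120. No section states h. Two statements suggest that it can be short. Section 11G says "2-D Echo will be performed at KD diagnosis (within 24h of IVIG infusion"), and a subject can qualify on that echo. Sections 11D1 and 11D2 schedule laboratory tests at "48 hours (not ESR as IVIG recently administered"). On the other side, 11B1 and 11B2 accept presentation up to 20 days after fever onset, so some subjects may enrol with resistance already known.

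**3. Model form.** Suppose the model adds c·R for resistance R, constant over time. In a change from baseline, (Y_t + cR) − (Y_0 + cR), the term cancels. A simulated four-visit model with a random intercept (marker loading 0.7, drug shift 1.0 in the notation of step 4) gave group-by-time effects of −0.672, −0.698 and −0.667 both with and without the term. With 15% of records missing, the estimates differed by at most 0.001. About 15% was lost when a covariate-by-time term was added or the group-by-time term was left out. The plan does not state which form it uses.

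**4. Size in a single-time-point model (illustration).** The documents give no resistance rate. Assumptions: latent inflammation is standard normal and is lowered by δ on drug. Resistance occurs when latent inflammation plus standard normal noise exceeds 0.8416 × √2 = 1.190, which gives p₀ = 20% in controls. The marker loads λ on latent inflammation. The total drug effect is −0.70 SD, groups are equal in size and baseline severity, and status is always settled after dosing.

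- z₀ = 0.8416; z₁ = (1.190 + δ)/√2; p₁ = 1 − Φ(z₁)
- Within-group slope of marker on resistance: γ = λ × {[φ(z₀) + φ(z₁)]/√2} / [p₀(1 − p₀) + p₁(1 − p₁)]
- Adjusted effect = −0.70 + γ(p₀ − p₁)

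For λ = 0.7 and δ = 1.0: z₁ = 1.549 and p₁ = 0.061. Then γ = 0.7 × (0.198 + 0.085)/(0.160 + 0.057) = 0.913, and the part removed is 0.913 × 0.139 = 0.127.

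| λ | δ | p₁ | γ | removed | adjusted effect | share removed |
|---|---|---|---|---|---|---|
| 0.5 | 0.4 | 13.0% | 0.636 | 0.044 | −0.656 | 6% |
| 0.7 | 0.5 | 11.6% | 0.896 | 0.075 | −0.625 | 11% |
| 0.7 | 1.0 | 6.1% | 0.913 | 0.127 | −0.573 | 18% |

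If status is always settled before dosing, the drug cannot change it, so p₁ = p₀ and nothing is removed.

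**5. Unequal baseline severity.** Let cases differ from controls by s in latent inflammation at baseline. The unadjusted effect is −0.70 + λs, and δ − s replaces δ above. The true effect stays at −0.70.

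| λ, δ | s = −0.3 (milder): unadjusted → adjusted | s = +0.3 (sicker): unadjusted → adjusted |
|---|---|---|
| 0.5, 0.4 | −0.85 → −0.78 | −0.55 → −0.54 |
| 0.7, 0.5 | −0.91 → −0.80 | −0.49 → −0.46 |
| 0.7, 1.0 | −0.91 → −0.76 | −0.49 → −0.39 |

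With milder cases, adjustment moves the estimate toward −0.70; with sicker cases, it moves it further away.

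**The case against.** The strongest reply is that harm does not follow automatically. Response to IVIG is only a covariate of interest and must pass the entry rule. No section documents an effect of the drug on fever. Controls are historical and unmatched on this variable, so it is a reasonable stand-in for severity. Unadjusted paired tests are planned beside the models. If the drug effect is read as change from baseline by group, a time-constant term removes nothing.

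All of this stands, and it limits the point. It does not remove it, because the plan neither fixes the model form nor separates resistance known before dosing from resistance that emerges afterwards.

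A reader might infer three stronger claims:

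- *That status is always settled after dosing.* The documents give no interval from IVIG to the first dose, and late presenters may enrol with resistance already known.
- *That the loss could approach a quarter.* With λ = 0.9 and δ = 1.0 the formula gives 23%. However, the effect through inflammation is then −0.90, so a total of −0.70 requires the drug to raise the marker directly by 0.20 SD. Nothing in the documents suggests that.
- *That infliximab, allowed at discretion under 14b, belongs to the same fault.* The covariate sentence does not name it, and its actual use is not given for either group. Adjusting for use after dosing would repeat the error described here.

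**Conclusion.** The point holds as a gap in specification. As written, 19B1 and 19B2 can adjust for a variable that is partly a result of study drug. Whether they would, and in which direction the estimate would move, cannot be settled from the documents.

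The 6–18% range rests on the assumed resistance rates, the −0.70 SD effect, equal baseline severity, status always settled after dosing, and a model that estimates a group main effect (or adds a covariate-by-time term). It is zero if status is always settled before dosing and essentially zero for a group-by-time effect with a time-constant covariate. With unequal baseline severity, adjustment can help or harm.

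Only secondary activity outcomes are affected. It would be wrong to infer that the primary safety outcome or the powered paired t-tests in 15A and 15B are compromised. This is a change worth considering, not a threat to the main conclusions.

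**What to change.** In 19B1 and 19B2, limit adjustment covariates to those fixed before the first dose of study drug. Replace the entry for response to IVIG with: *IVIG-resistance status established before the first dose (resistant / not resistant / not yet evaluable; controls classified at the same time after the end of IVIG as the matched case's first dose).* Add: *A model that includes resistance established later is reported only as a labelled sensitivity analysis.* The third category keeps subjects whose window is still open apart from true responders.

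The cost is SAP wording, one extra model, and a check of control records for the end of IVIG and the time at which resistance was established. No sample size, power or alpha changes. The main drawback is that if most first doses come before 36 hours after IVIG, nearly everyone is not yet evaluable. The main model then has little or no adjustment for response to IVIG, and the sensitivity model carries it.
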